9.6.3 Statistical Methods for Safety Analysis (Phase 1 and Phase 2)

Safety and tolerability will be assessed by clinical review of all relevant parameters, including AEs, postvaccination temperature measurements, and laboratory measurements (Phase 1 only). Safety analyses will be conducted separately for Phase 1 and Phase 2.

The analysis of AEs and temperature measurements will follow a tiered approach ([Table 9](#)). The tiers differ with respect to the analyses that will be performed. Events are either prespecified as Tier 1 events or will be classified as belonging to Tier 2 or Tier 3 based on the number of events observed.

Laboratory measurements collected during Phase 1 (see Appendix 2) will be summarized separately. Details regarding the analysis of laboratory measurements will be provided in the sSAP.

Tier 1 Events

Safety events or AEs of special interest that are identified a priori constitute Tier 1 events that will be subject to inferential testing for statistical significance with p-values and 95% CIs provided for between-treatment differences in the proportion of participants with events.

No Tier 1 events are defined for this study.

This study will solicit for predefined injection-site and systemic AEs. However, as this is the first clinical study of pPCV, no data exists around which a comparative, data-driven safety hypothesis can be formulated and tested. As a result, the solicited injection-site and systemic AEs reported in this study will be analyzed as Tier 2 events.

Tier 2 Events

Tier 2 events will be assessed via point estimates and risk differences with 95% CIs provided for differences in the proportion of participants with events; these analyses will be performed using the M&N method [Miettinen, O. and Nurminen, M. 1985], an unconditional, asymptotic method.

For this study, solicited injection-site AEs from Day 1 through Day 5 postvaccination, solicited systemic AEs from Day 1 through Day 5 postvaccination, and temperature measurements collected from Day 1 through Day 5 postvaccination are considered Tier 2 events. In addition, the broad AE categories consisting of the percentage of participants with any AE, any vaccine-related AE, any solicited injection-site AE, any solicited systemic AE, any SAE, any vaccine-related SAE, and death will be considered Tier 2 events. Nonserious AEs will be followed for 30 days postvaccination, while SAEs will be followed through the duration of participation in the study.

9.6.4 Summaries of Demographic and Baseline Characteristics

The comparability of the vaccination groups for each relevant demographic and baseline characteristic will be assessed using summary tables. No statistical hypothesis tests will be

performed on these characteristics. The number and percentage of participants randomized and vaccinated, and the reasons for discontinuation, will be displayed by group. Demographic variables (eg, age) and prior and concomitant therapies and vaccines will be summarized by group. Separate summaries will be provided for Phase 1 and Phase 2.

No other analyses are planned for this study.

9.7 Interim Analyses

A review of Phase 1 and Phase 2 safety and tolerability data will be conducted by an unblinded siDMC. Immunogenicity data will also be provided to the siDMC to enable a benefit-risk assessment. A description of the structure and function of the siDMC, along with the timing and content of the safety review, will be outlined in the siDMC charter. Information regarding the composition of the siDMC is provided in Appendix 1.

Blinding to intervention assignment will be maintained at all investigational sites. Participant-level unblinding will be restricted to an internal unblinded statistician and statistical programmer performing any planned or requested safety reviews by the siDMC. Any safety reviews conducted while the study is ongoing will be provided by the internal unblinded statistician to the siDMC. Prior to final study unblinding, the internal unblinded statistician will not be involved in any discussions regarding modifications to the protocol, statistical methods, identification of protocol deviations, or data validation efforts after the safety reviews.

Two prespecified analyses are planned prior to the completion of this study, as described below.

9.7.1 Phase 1 Interim Analysis

An interim analysis will be performed once the primary 30-day postvaccination safety and immunogenicity data are available for all Phase 1 participants. At this point, the database will be locked and an analysis will be performed to summarize the safety and immunogenicity data. This analysis will not occur until medical/scientific review of the data has been performed and protocol deviations have been identified. The siDMC will review unblinded Phase 1 safety and immunogenicity data reports and evaluate the benefit and risk profile to make a recommendation regarding proceeding to Phase 2. The Sponsor study team will review the Phase 1 safety and immunogenicity aggregate data reports to inform the clinical development decision to proceed to Phase 2. The Sponsor study team will not be unblinded to participant-level data. The unblinded Phase 1 data will be provided by an unblinded statistician who is not part of the blinded study team, and the clinical database will remain blinded to both the Sponsor study team and participating sites throughout the duration of the Phase 1/Phase 2 study. Additionally, based on the analysis of this Phase 1 data, power and sample size assumptions for Phase 2 will be examined and the sample size may be adjusted.

9.7.2 Phase 2 Interim Analysis

An interim analysis is planned to support clinical development decisions prior to the completion of the Phase 2 portion of this study. This analysis will be conducted once the primary 30-day postvaccination safety and immunogenicity data are available for all Phase 2 participants and the 6-month safety data are available for at least 50% of Phase 2 participants. This analysis will represent the final analysis of the primary immunogenicity endpoints and will be considered a preliminary analysis of the safety data. These analyses will be conducted by an unblinded statistician who is not part of the blinded study team. The siDMC will review unblinded Phase 2 safety and immunogenicity data reports and evaluate the benefit and risk profile. The Sponsor study team will review the Phase 2 safety and immunogenicity aggregate data reports to inform further clinical development. The Sponsor study team will not be unblinded to participant-level data.

9.8 Multiplicity

As described in Section 9.6.2, there are 2 types of hypothesis tests for the Phase 2 immunogenicity analysis: (1) a separate noninferiority test for each of the common serotypes between pPCV and PNEUMOVAX™23, and (2) a separate superiority (ie, statistically significantly greater) test for each of the serotypes that are unique to pPCV. This study will be considered to have met its primary immunogenicity objective if success is demonstrated for all common serotypes and all unique serotypes included in the primary immunogenicity hypotheses. The intersection-union test controls the overall type I error at the 1-sided 0.025 level within each group; therefore, no multiplicity adjustment will be required within each group [Berger, R. L. 1982]. The intersection-union test refers to the fact that the set of statistical null hypotheses to be tested can be expressed as a union, and the set of statistical alternative hypotheses as an intersection. Thus, the overall statistical null hypothesis can only be rejected if each of the set of statistical null hypotheses are rejected.

The same multiplicity strategy will be applied to the 2 secondary study hypotheses for which there is also a noninferiority hypothesis for the common serotypes between pPCV and PNEUMOVAX™23, and a superiority (ie, statistically significantly greater) hypothesis for the serotypes unique to pPCV, as measured by IgG. In this way, for the secondary hypotheses to be supported by the data, all statistical tests will have to be statistically significant. This approach controls the type I error at 0.025 (1-sided) for the set of primary hypothesis tests and separately at 0.025 (1-sided) for the set of secondary hypothesis tests.

No multiplicity adjustments will be made for the safety comparisons.

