Statistical Methods for Key Immunogenicity Analyses in Phase 1	
Immunogenicity analyses will be conducted separately for each serotype. Immunogenicity endpoints will be analyzed at 30 days postvaccination compared with prevaccination (Day 1) to describe the IgG antibody concentrations in response to the vaccination. The ratio of OPA GMTs and IgG GMCs (pPCV-1/PNEUMOVAX™23 and pPCV-2/PNEUMOVAX™23) will be presented along with 95% CIs by vaccination group.
 
The OPA GMT ratio estimation and 95% CI will be calculated using a cLDA method.

Statistical Methods for Key Immunogenicity Analyses in Phase 2	
Immunogenicity analyses will be conducted separately for each serotype. To address the primary noninferiority hypothesis (H1), a noninferiority test comparing OPA GMTs for the common serotypes in pPCV and PNEUMOVAX™23 (control group) will be conducted. A noninferiority margin of 0.33 corresponding to a 3.0-fold lower OPA GMT in the pPCV group compared with the control group will be used. Rejecting the null hypothesis at the 1-sided $\alpha=0.025$ level corresponds to the lower bound of

	
the 2-sided 95% CI on the GMT ratio (pPCV/control) being >0.33 and would lead to the conclusion that the OPA GMT for pPCV is noninferior to that of the control vaccine, for the given common serotype.
 
To address the second primary hypothesis (H2), a test comparing OPA GMTs for the serotypes unique to pPCV will be conducted. Rejecting the null hypothesis at the 1-sided $\alpha=0.025$ level corresponds to the lower bound of the 2-sided 95% CI on the GMT ratio (pPCV/control) being >1.0 and would lead to the conclusion that the OPA GMT for pPCV is statistically significantly greater than that of the control vaccine, for the given unique serotype.
 
The statistical margins specified for H1 and H2 are consistent with previous early phase comparative studies [Jackson, L. A., et al 2013].
 
The OPA GMT ratio estimation, 95% CI, and the hypothesis test (ie, 1-sided p-value) will be calculated using a cLDA method.

Statistical Methods for Key Safety Analyses in Phase 1 and Phase 2	
The analysis of safety will follow a tiered approach. No Tier 1 events are defined in this study. For Tier 2 events, 95% CIs will be provided for between-group differences in the proportion of participants with events; these analyses will be performed using the M&N method [Miettinen, O. and Nurminen, M. 1985].

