9.6 Statistical Methods

No statistical hypothesis testing is planned for Phase 1, but rather estimation will be performed for both the safety and immunogenicity data.

For immunogenicity analyses in Phase 2, unless otherwise specified, all statistical tests will be conducted at the $\alpha=0.05$ level (2-sided). Results that will be considered statistically significant (versus nominally significant) after consideration of the strategy for controlling type-I errors are described in Section 9.8.

9.6.1 Statistical Methods for Immunogenicity Analyses in Phase 1

The immunogenicity analyses will be conducted for each serotype separately.

The geometric mean ratios and 95% CIs of IgG GMCs and OPA GMTs will be calculated using a cLDA method proposed by Liang and Zeger [Liang, K-Y and Zeger, S. L. 2000] utilizing data from all 3 vaccination groups. In this model, the response vector consists of the

log-transformed prevaccination (Day 1) and postvaccination (Day 30) antibody titers. The repeated measures model will include terms for time, the interaction of time-by-vaccination group (with a restriction of the same baseline mean across groups). The treatment difference in terms of a geometric mean ratio at a given postvaccination time point will be estimated and tested from this model. The term for time will be treated as a categorical variable. An unstructured covariance matrix will be used to model the correlation among repeated measurements. This model allows the inclusion of participants who are missing either the baseline or postbaseline measurements, thereby increasing efficiency. The GMFRs from prevaccination to 30 days postvaccination for both OPA and IgG response will be estimated by vaccination group, and the corresponding 95% CIs will be based on the sample t-distribution.

The analysis strategy for key immunogenicity variables in Phase 1 is listed in [Table 7](#).

Table 7 Analysis Strategy for Key Immunogenicity Variables in Phase 1

Endpoint/Variable (Description, Time point)	Statistical Method	Analysis Population	Missing Data Approach
Secondary Endpoints			
Ratio of IgG GMCs at 30 days postvaccination for common serotypes	cLDA ^a (point estimate, 95% CI)	PP/FAS	Model-based
Ratio of OPA GMTs at 30 days postvaccination for common serotypes	cLDA ^a (point estimate, 95% CI)	PP/FAS	Model-based
Ratio of OPA GMTs at 30 days postvaccination for unique serotypes in pPCV	cLDA ^a (point estimate, 95% CI)	PP/FAS	Model-based

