GMFRs from prevaccination to 30 days postvaccination for both OPA and IgG responses	Descriptive Statistics (point estimate, 95% CI)	PP/FAS	Missing data will not be imputed

CI = confidence interval; cLDA = constrained longitudinal data analysis; FAS = Full Analysis Set; GMC = geometric mean concentration; GMFR = geometric mean fold rise; GMT = geometric mean titer; IgG = immunoglobulin G; OPA = opsonophagocytic activity; PP = Per-protocol.

^a cLDA model with terms for time and the interaction of time-by-vaccination group.

9.6.2 Statistical Methods for Immunogenicity Analyses in Phase 2

This section describes the statistical methods that address the primary and secondary Phase 2 immunogenicity objectives. The margins of noninferiority and superiority (ie, statistically significantly greater) presented below are consistent with previous early phase comparative studies [Jackson, L. A., et al 2013].

The immunogenicity analyses will be conducted for each serotype separately.

Primary Endpoints/Hypotheses

For the common serotypes, the primary noninferiority hypotheses (H1) regarding OPA GMT levels between recipients of pPCV and PNEUMOVAXTM23 is:

$$\begin{aligned} H_0: \text{GMT}_1/\text{GMT}_2 &\leq 0.33 \text{ versus} \\ H_1: \text{GMT}_1/\text{GMT}_2 &> 0.33 \end{aligned}$$

where GMT_1 is the serotype-specific OPA GMT for the pPCV group and GMT_2 is the serotype-specific OPA GMT for the PNEUMOVAXTM23 group. A ratio of 0.33 corresponds to a 3.0-fold lower OPA GMT in the pPCV group compared with the PNEUMOVAXTM23 group. Rejecting the null hypothesis (H_0) at the 1-sided $\alpha=0.025$ level corresponds to the lower bound of the 2-sided 95% CI on the GMT ratio (pPCV/PNEUMOVAXTM23) being >0.33 and would lead to the conclusion that the OPA response to pPCV for the common serotype is noninferior to that of PNEUMOVAXTM23.

For the serotypes that are unique to pPCV, the primary superiority (ie, statistically significantly greater) hypotheses (H2) regarding OPA levels between recipients of pPCV group and PNEUMOVAXTM23 group is:

$$\begin{aligned} H_0: \text{GMT}_1/\text{GMT}_2 &\leq 1.0 \text{ versus} \\ H_1: \text{GMT}_1/\text{GMT}_2 &> 1.0 \end{aligned}$$

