where GMT_1 is the OPA GMT for the pPCV group and GMT_2 is the OPA GMT for the PNEUMOVAXTM23 group. Rejecting the null hypothesis (H_0) at the 1-sided $\alpha=0.025$ level corresponds to the lower bound of the 2-sided 95% CI on the GMT ratio (pPCV/PNEUMOVAXTM23) being >1.0 and would lead to the conclusion that the OPA response to pPCV for the unique serotype is statistically significantly greater than that of PNEUMOVAXTM23.

The GMT ratio estimation, 95% CI, and the hypothesis test (ie, 1-sided p-value) will be calculated using a cLDA method proposed by Liang and Zeger [Liang, K-Y and Zeger, S. L. 2000] utilizing data from both vaccination groups. In this model, the response vector consists of the log-transformed prevaccination (Day 1) and postvaccination (Day 30) antibody titers. The repeated measures model will include terms for time, the interaction of time-by-vaccination group (with a restriction of the same baseline mean across groups), age stratum (ie, 50 to 64 years, 65 to 74 years, and ≥ 75 years) at vaccination, and age stratum-by-time interaction. This model will allow for different baseline means for each age stratum, but restrict the baseline mean within each age stratum to be the same for all vaccination groups. The treatment difference in terms of a geometric mean ratio at a given postvaccination time point will be estimated and tested from this model. The term for time will be treated as a categorical variable. An unstructured covariance matrix will be used to model the correlation among repeated measurements. The Kenward-Roger adjustment will be used with REML to make proper statistical inference. This model allows the inclusion of

participants who are missing either the baseline or postbaseline measurements, thereby increasing efficiency.

For titer measurements that are smaller than the lower bound of the assay's detectable range, half of the lower bound will be used as the value of the titer.

Secondary Endpoints/Hypotheses

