The same statistical approach as used for the primary endpoints will be used to address the secondary immunogenicity hypotheses (H3 and H4) that compare the IgG GMC responses of pPCV with PNEUMOVAXTM23, except that a noninferiority margin of 0.5 will be used to evaluate noninferiority of the common serotypes, which corresponds to a 2.0-fold lower IgG GMC in the pPCV group compared with the PNEUMOVAXTM23 group. The GMFRs from prevaccination to 30 days postvaccination for both OPA and IgG response will be estimated by vaccination group, and the corresponding 95% CIs will be based on sample t-distribution. The difference between the pPCV group and the PNEUMOVAXTM23 group in the proportion of participants with ≥ 4 -fold increase in serotype-specific OPA responses from prevaccination (Day 1) to 30 days postvaccination will be estimated. The corresponding 95% CIs about these differences will be calculated using the M&N method, stratifying by age at enrollment (50 to 64 years, 65 to 74 years, and ≥ 75 years) [Miettinen, O. and Nurminen, M. 1985].

The analysis strategy for key immunogenicity variables in Phase 2 is listed in [Table 8](#).

Table 8 Analysis Strategy for Key Immunogenicity Variables in Phase 2

Endpoint/Variable (Description, Time point)	Statistical Method	Analysis Population	Missing Data Approach
Primary Endpoints			
Ratio of OPA GMTs at 30 days postvaccination for common serotypes	cLDA ^a (point estimate, 95% CI, p-value ^b)	PP/FAS	Model-based
Ratio of OPA GMTs at 30 days postvaccination for unique serotypes	cLDA ^a (point estimate, 95% CI, p-value ^b)	PP/FAS	Model-based
Secondary Endpoints			
Ratio of IgG GMCs at 30 days postvaccination for common serotypes	cLDA ^a (point estimate, 95% CI, p-value ^b)	PP/FAS	Model-based
Ratio of IgG GMCs at 30 days postvaccination for unique serotypes	cLDA ^a (point estimate, 95% CI, p-value ^b)	PP/FAS	Model-based
GMFRs from prevaccination to 30 days postvaccination for both OPA and IgG responses	Descriptive Statistics (point estimate, 95% CI)	PP/FAS	Missing data will not be imputed
Difference in proportion of participants with a ≥ 4 -fold increase in serotype-specific OPA responses from prevaccination to 30 days postvaccination	Descriptive Statistics (point estimate, 95% CI)	PP/FAS	Missing data will not be imputed

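### Must Section 9.8 say whether a serotype that passes in a set not fully met is statistically or only nominally significant?

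*Combined protocol and SAP*

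**What the plan says.** Section 9.6 (Statistical Methods) sets the Phase 2 test level and then points forward: "Results that will be considered statistically significant (versus nominally significant) after consideration of the strategy for controlling type-I errors are described in Section 9.8".

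Section 9.8 (Multiplicity) describes one test per serotype: noninferiority for each common serotype and, for the others, "a separate superiority (ie, statistically significantly greater) test for each of the serotypes that are unique to pPCV". The primary objective is met only if every common and every unique serotype succeeds. The justification is the intersection-union principle: "the overall statistical null hypothesis can only be rejected if each of the set of statistical null hypotheses are rejected". The IgG hypotheses follow the same rule: "for the secondary hypotheses to be supported by the data, all statistical tests will have to be statistically significant". Type I error is stated to be held at one-sided 0.025 for the primary set and, separately, for the secondary set.

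The per-serotype wording sits elsewhere. In the Section 9.1 summary, a lower confidence bound above 1.0 supports the conclusion that the OPA GMT for pPCV "is statistically significantly greater than that of the control vaccine, for the given unique serotype". Section 9.6.2 says that rejecting the null for a common serotype "would lead to the conclusion that the OPA response to pPCV for the common serotype is noninferior", and for a unique serotype "would lead to the conclusion that the OPA response to pPCV for the unique serotype is statistically significantly greater". Section 9.6.2 carries the same approach over to IgG under H3 and H4, with a noninferiority margin of 0.5 in place of 0.33.

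**The concern.** A reader who follows the pointer from Section 9.6 does not find the word nominal in Section 9.8. The section says when an objective is met. It does not say how to describe the serotypes that passed when the objective was missed. Its sentence on the secondary hypotheses applies the term statistically significant to each single test, and Sections 9.1 and 9.6.2 attach a conclusion to one serotype without any condition on the others.

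If one IgG serotype misses, the remaining serotypes could then be reported either as formally noninferior or superior, or as descriptive results. If the formal reading were taken, the intersection-union argument would no longer protect the statements made, because it controls only the claim that all tests pass. The choice of label might also be made with results in view.

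**Working it through.** **1. Reproduce the plan's powers (Section 9.9.1).** Inputs: 225 evaluable per group; SD of natural-log IgG 1.73 and of OPA 2.2; true ratio 1 for common serotypes; true ratio 2 (IgG) and 3 (OPA) for unique serotypes. Margins from Section 9.6.2: 0.5 (IgG) and 0.33 (OPA). One-sided level 0.025.

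The standard error of a log ratio is SD × √(2/225). Power per IgG serotype, the same for common and unique because the log distance is ln 2 in both:

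Φ(ln 2 / (1.73 × √(2/225)) − 1.96) = Φ(4.25 − 1.96) = 0.98898.

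The documents leave the serotype sets to the sSAP. Under independence, the stated set powers imply these counts:

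- common: ln 0.87 / ln 0.98898 = 12.6
- unique: ln 0.92 / ln 0.98898 = 7.5

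I take 13 and 8 as an assumption. They give 0.98898^13 = 0.866 and 0.98898^8 = 0.915, against the stated 87% and 92%. The products of the stated powers agree with the plan: 0.87 × 0.92 = 0.800 and 0.987 × 0.992 = 0.979.

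The counts do not fit the OPA figures. Power per OPA serotype is about 0.9996, so 13 and 8 would give about 99.5% and 99.7%, not 98.7% and 99.2%. Solving the OPA powers gives about 31 to 37 common serotypes (margin taken as 1/3 or 0.33) and 19 unique. Results below that use 13 and 8 are illustrative.

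**2. How often the question arises.** It arises when a set is not fully met, which is 1 minus the stated power:

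| | Common | Unique | Either |
|---|---|---|---|
| IgG, independent tests | 13% | 8% | 1 − 0.87 × 0.92 = 20% |
| OPA, independent tests | 1.3% | 0.8% | 1 − 0.987 × 0.992 = 2.1% |

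All serotypes are measured in the same participants, so positive correlation is likely. The documents give none, so I show a range. With exchangeable normal test statistics, counts 13 and 8, and per-serotype power set to match the stated powers, the chance of any IgG miss is 11% at correlation 0.5 and 8% at 0.7. For OPA it is 1.5% and 1.0%.

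**3. How many serotypes would then need a label.** With all-pass probability A in a set of k, the mean number passing in a failed set is k × (0.98898 − A)/(1 − A). At correlation 0, 0.5 and 0.7 this gives 11.9, 11.3 and 10.7 of 13 common serotypes, and 7.0, 6.6 and 6.1 of 8 unique ones.

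**4. Which label the text supports.**

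- Section 9.6 defines the split by what remains significant once the error-control strategy has been considered.
- Section 9.8 gives that strategy, and it controls error for the set only.
- A single result in an unmet set is outside that control, so under Section 9.6 it is nominal.

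The arithmetic agrees. If each serotype result were read as a formal claim, with every null true and tests independent, the chance of at least one false claim would be 1 − 0.975^13 = 28% for 13 tests and 1 − 0.975^8 = 18% for 8. Neither is compatible with the 0.025 that Section 9.8 says it controls.

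**5. The wording that seems to point the other way.** The phrase about being statistically significantly greater is the protocol's standing gloss on superiority, used again in Sections 9.1, 9.6.2 and 9.9.1. It names a type of hypothesis. The per-serotype sentences in 9.1 and 9.6.2 explain how a one-sided rejection maps to a confidence bound; they define the component test and leave multiplicity to Section 9.8. The sentence on the secondary hypotheses is the all-or-none rule itself, and calling a component of an intersection-union test significant is ordinary usage.

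**The case for a change.** The best case for a change is that an inference is not a statement. Section 9.6 promises that Section 9.8 describes the split, and it does so only by implication. For safety the plan does not rely on inference: Section 9.6.3 says outright that the unadjusted intervals are descriptive. Immunogenicity has no matching sentence. Section 9.7.2 lets the study team see aggregate Phase 2 results at the analysis that is final for the primary immunogenicity endpoints, and one sentence would cost almost nothing.

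The observation about the wording stands. So does a related point: Section 9.8 speaks both of control within each group and of control for the primary hypothesis tests as a set. If all common serotypes passed and a unique one failed, the text does not say whether the common set keeps its formal status. A sentence that made results nominal in an unmet set, without defining the set, would leave that open.

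What does not stand is that two readings have equal support, or that the choice must wait for the results. Only one reading fits the stated error control. The plan also provides for an sSAP before database lock, which already has to define the serotype sets. It is not among the documents, so it cannot be assumed to settle the label, nor assumed to leave it open.

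**Conclusion.** No change to the plan follows. This is a small gap in wording that analysts would fill correctly from Sections 9.6 and 9.8 read together: serotype results in a set that is not fully met are nominal. The most it could affect is the adjective used for individual serotypes in the report. That would arise mainly for IgG, in at most about 20% of trials under the plan's own powers (13% common, 8% unique), and in about 8 to 11% at correlations of 0.7 to 0.5; for OPA it is about 2% or less. These frequencies are essentially 1 minus the stated power and do not measure wrong decisions. They assume the planning ratios and SDs hold; the correlated figures and the numbers of passing serotypes also rest on the assumed counts of 13 and 8. The tests, intervals, set-level error of 0.025, power, sample size and success rule are the same whether or not the label is spelled out, so following the plan as written gives sound conclusions on its objectives.
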